--	---

	
reasons and timing of the missing data will be summarized by treatment groups. In the primary analysis, all observed data will be used regardless of treatment adherence or increase of asthma background medication. No imputation will be conducted for the missing severe exacerbation information after a patient prematurely withdraws from the study up to Week 52. In addition, sensitivity analyses based on pattern mixture model, placebo based pattern mixture model and tipping point analysis based on the same negative binomial model as being used in the primary analysis may be conducted to assess the robustness of the conclusion of the main model. Details of these sensitivity analyses will be described in the SAP.
 
Analysis of other secondary endpoints
 
The change from baseline for continuous endpoints will be analyzed using a mixed-effect model with repeated measures (MMRM) approach. The model will include change from baseline as response variables, and for treatment, age, weight (≤ 30kg, > 30kg), region, baseline eosinophil level (< 300 cells/μL, ≥ 300 cells/μL), baseline FeNO level (< 20 ppb, ≥ 20 ppb), baseline ICS dose level (medium/high), visit, treatment-by-visit interaction, baseline value, and baseline-by-visit interaction as covariates; unless otherwise specified (details will be documented in SAP). Sex, height, and ethnicity will also be included as covariates in the models for spirometry parameters. An unstructured correlation matrix will be used to model the within-patient errors. Parameters will be estimated using restricted maximum likelihood method using the Newton-Raphson algorithm. Statistical inferences on treatment comparisons for the change from baseline at Weeks 12 will be derived from the mixed-effect model with Kenward and Roger degree of freedom adjustment approach. Treatment comparisons at other timepoints, 8, 12, 24, 36 and 52 Week and other timepoints in between will also be provided from the mixed-effect model for descriptive purpose. Data up to Week 52 will be included as response variables.
 
Time to first severe asthma exacerbation event and time to first LOAC will be analyzed using a Cox regression model with time-to-event as the dependent variable, and treatment, age, weight (≤ 30kg, > 30kg), region, baseline eosinophil level (< 300 cells/μL, ≥ 300 cells/μL), baseline FeNO level (< 20 ppb, ≥ 20 ppb), baseline ICS dose level (medium/high) and number of asthma events prior to the study as covariates. The estimated hazard ratio (dupilumab versus placebo) along with its 95% confidence interval will be presented. The Kaplan-Meier method will be used to derive the proportion of patients with a severe asthma exacerbation event at Weeks 12, 24, 36, and 52, specific to each treatment group.
 
The safety variables, including AEs, laboratory parameters, vital signs, ECG, and physical examinations will be summarized using descriptive statistics.
 
The analysis of safety variables will be performed based on the safety population.
 
Interim Analysis
 
There is no interim analysis planned for this study.
 
Planned database lock
 
The database lock is planned based on the time when all randomized patients reach complete week 52 visit or discontinue from the study before week 52. Analyses will be based on all data collected up to this database lock and will be considered as the final analyses in the CSR (Clinical Study Report). Additional data between database lock and last patient completing last visit will be summarized in a CSR addendum.

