11.4.2.2 Analyses of Secondary Efficacy Endpoints

11.4.2.2.1 Analysis of Change from Baseline in Pre-bronchodilator % Predicted FEV1

The key secondary endpoint, change from baseline in pre-bronchodilator % predicted FEV1 at Week 12, will be analyzed using a mixed-effect model with repeated measures (MMRM) approach. The analysis for the key secondary endpoint will be performed in the type 2 inflammatory phenotype, baseline blood eosinophils ≥ 300 cells/ μL , baseline blood eosinophils ≥ 150 cells/ μL , baseline FeNO ≥ 20 ppb, and full ITT populations. When performing the key secondary endpoint analysis in the type 2 inflammatory phenotype, baseline blood eosinophils ≥ 150 cells/ μL , or the full ITT populations, the model will include change from baseline as response variables, and for treatment, age, weight ($\leq 30\text{kg}$, $>30\text{kg}$), region, baseline eosinophil level (<300 cells/ μL , ≥ 300 cells/ μL), baseline FeNO level (<20 ppb, ≥ 20 ppb), baseline ICS dose level (medium/high), visit, treatment by-visit interaction, baseline value, and baseline-by-visit interaction as covariates. When performing the analysis in the baseline blood eosinophils ≥ 300 cells/ μL population, the baseline eosinophil level will be removed from the model

covariates. When performing the analysis in the baseline FeNO ≥ 20 ppb population, the baseline FeNO level will be removed from the model covariates. Sex, height and ethnicity will also be included as covariates in the models for spirometry parameters. An unstructured correlation matrix will be used to model the within-patient errors. Parameters will be estimated using restricted maximum likelihood method using the Newton-Raphson algorithm. Statistical inferences on treatment comparisons for the change from baseline at Weeks 12 will be derived from the mixed-effect model with Kenward and Roger degree of freedom adjustment approach. Treatment comparisons at other timepoints, 8, 12, 24, 36 and 52 week and other timepoints in between will also be provided from the mixed-effect model for descriptive purpose. Data up to Week 52 will be included as response variables.

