11.4.2.2.3 Analysis of Change from Baseline for Other Continuous Variables

The change from baseline for other continuous endpoints will be analyzed using MMRM in the same fashion as for the endpoint of pre-bronchodilator % predicted FEV1. The covariates to be included are treatment, age, weight (≤ 30 kg, > 30 kg), region, baseline eosinophil (< 300 cells/ μ L, ≥ 300 cells/ μ L), baseline FeNO level (< 20 ppb, ≥ 20 ppb), baseline ICS dose level (medium/high), visit, treatment-by-visit interaction, corresponding baseline value and baseline-by-visit interaction. Sex and height will be included as covariates in the models, if the endpoint belongs to spirometry parameters. Descriptive statistics including number of patients, mean, standard error and LS means will be provided for each timepoint. In addition, differences in LS means, the corresponding 95% CI and the p-value will be derived from the MMRM model for comparison of dupilumab against placebo at each timepoint.

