1.6 STATISTICAL MODIFICATIONS MADE IN THE STATISTICAL ANALYSIS PLAN

This Statistical Analysis Plan (SAP) for study EFC14153 is based on the protocol dated 18 October 2019. This section summarizes major changes to the statistical analysis features in the SAP.

Table 2 - Major changes in statistical analysis plan

SAP Version	Approval Date	Changes	Rationale
1.0	23-OCT-2019	Not Applicable	Original version
2.0	Current version	Elaboration of Estimand Analysis of systemic corticosteroid exposure	Clarification per FDA's recommendation. To evaluate efficacy of Dupilumab in reducing exposure to systemic corticosteroids
		Addition of the analysis of the annualized rate of loss of asthma control (LOAC)	To evaluate efficacy of Dupilumab in reducing Loss of Asthma Control (LOAC) events
		COVID19 pandemic relevant analysis:	To evaluate the impact of COVID19 pandemic on study conduct.
		Subgroup analysis, treatment exposure adjusted analysis for key adverse event endpoints	To further evaluate the safety of Dupilumab in subgroups of interest; To evaluate the safety of Dupilumab taking the duration of exposure into consideration.
		For analysis of Pre-bronchodilator % predicted FEV1, covariates of age, sex, and baseline height are removed from the model	The effect of age, sex, and height on the predicted FEV1 have already been accounted for in the predicted FEV1 calculation equation.

SAP Version	Approval Date	Changes	Rationale
		Add treatment-by-biomarker analysis for annualized severe exacerbation rate during the 52 week treatment period to explore FeNO's independent predictability of Dupilumab's treatment effect	Per FDA recommendation.
		Add treatment-by-biomarker analysis for Pre-bronchodilator % predicted FEV1 change from baseline at Week to explore FeNO's independent predictability of Dupilumab's treatment effect	Per FDA recommendation.
		Add quadrant analysis using different FeNO cutoff values	Per FDA recommendation.
		Remove subgroup analysis by baseline age group (6-8, 9-11 years)	Not a meaningful subgroup analysis.
		Remove subgroup analysis by Elevated IgE (Yes/No)	This is already a subgroup to evaluate the baseline IgE level, ie, Total IgE ((<100 IU/mL, ≥100 IU/mL)

Table 3 - Changes to the planned analysis approach in the protocol

SAP Version	Approval Date	Planned analysis in the protocol	Analysis in the statistical analysis plan	Rationale

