2.0	Current version	When performing the key secondary endpoint analysis in the Type 2 inflammatory asthma phenotype, baseline blood eosinophils ≥0.15 Giga/L, and full ITT populations, the model will include change from baseline in % predicted FEV1 values up to Week 12 as response variables, and treatment, age, baseline weight, region, sex, ethnicity, baseline height, baseline eosinophil level, baseline FeNO level, baseline ICS dose level, visit, treatment by-visit interaction, baseline % predicted FEV1 value and baseline-by-visit interaction as covariates.	
The model covariates are updated by removing age, sex, and baseline height:
 
When performing the key secondary endpoint analysis in the Type 2 inflammatory asthma phenotype, baseline blood eosinophils ≥0.15 Giga/L, and full ITT populations, the model will include change from baseline in % predicted FEV1 values up to Week 12 as response variables, and treatment, baseline weight, region, ethnicity, baseline eosinophil level, baseline FeNO level, baseline ICS dose level, visit, treatment by-visit interaction, baseline % predicted FEV1 value and baseline-by-visit interaction as covariates.
	The effect of age, sex, and height on the predicted FEV1 have already been accounted in the predicted FEV1 calculation equation.

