2.1.3.2 Secondary efficacy endpoint(s)

The key secondary endpoint of this study is the change from baseline in pre-bronchodilator % predicted FEV1 at Week 12.

The other secondary efficacy endpoints include:

- Change from baseline in pre-bronchodilator % predicted FEV1 at Weeks 2, 4, 8, 24, 36, and 52 and other time points assessed
- Time to first severe exacerbation event during 52-week treatment period
- Time to first LOAC Event during 52-week treatment period
- Change from baseline in other lung function measurements (absolute and relative FEV1, AM/PM peak expiratory flow, FVC, forced expiratory flow (FEF) 25-75%, post-bronchodilator % predicted FEV1) at Weeks 2, 4, 8, 12, 24, 36, 52, and other time points assessed
- The effect of dupilumab on healthcare resource utilization (HCRU)
- Change from Baseline at Weeks 2, 4, 8, 12, 24, 36, and 52 and other timepoints in:
 - Morning/evening asthma symptom score (electronic diary)
 - PRO:
 - ACQ-IA, for children 6 to <12 years old,
 - Use of reliever medication
 - Number of nocturnal awakenings due to asthma symptoms requiring the use of reliever medication
- Change from Baseline at Weeks 12, 24, 36, 52, 64 in:
 - PRO:
 - Paediatric Asthma Quality of Life Questionnaire with Standardised Activities–Interviewer Administered (PAQLQ(S) IA) score, for children ≥ 7 to <12 years old at Randomization Visit 2

LOAC event during the study is defined as any of the following:

- ≥ 6 additional reliever puffs of salbutamol/albuterol or levosalbutamol/levalbuterol in a 24 hour period (compared to baseline) on 2 consecutive days or
- Increase in ICS dose ≥ 4 times than the dose at Visit 2 or
- A decrease in AM or PM peak flow of 30% or more on 2 consecutive days of treatment, based on the defined stability limit. The treatment period stability limit is defined as the respective mean AM or PM PEF obtained over the last 7 days prior to randomization (Day 1); or
- Severe exacerbation event

Two events will be considered as different if the interval between their start dates is equal or greater than 28 days.

If a patient has an event during the 52-week treatment period, regardless the patient is on the study treatment or discontinues the study treatment but remains in the study, the time to first severe exacerbation event/first LOAC event is defined as (onset date of the first severe exacerbation/LOAC event – randomization date +1).

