In the Type 2 inflammatory asthma phenotype and baseline blood eosinophils ≥ 0.3 Giga/L populations, change from baseline for other continuous endpoints at all time-points will be analyzed using MMRM model including measurements up to Week 52. The model will include change from baseline of these endpoints from all available planned time points up to Week 52 as response variables, regardless if the patient is on treatment or not when the endpoint is measured. When performing these analyses in the Type 2 inflammatory asthma phenotype population, treatment, age, baseline weight, region (pooled country), baseline eosinophil level, baseline FeNO level, baseline ICS dose level, visit, treatment by-visit interaction, baseline endpoint value and baseline-by-visit interaction will be the model covariates. When performing these analyses in the baseline blood eosinophils ≥ 0.3 Giga/L population, the baseline eosinophil level will be removed from the model covariates. Ethnicity will be included as the covariate only in the models for spirometry parameters, specifically. Differences in LS means, the corresponding 95% CI and the p-value will be provided for comparison between dupilumab and placebo along with descriptive statistics.

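### SAP 2.4.4.3.1 drops sex and height from the models for spirometry endpoints not expressed as % predicted, and the only reason it logs does not fit those endpoints

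*SAP*

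**What the plan says.** **Protocol.** The rule appears in three places.
- Section 11.4.2.2.3, the counterpart of SAP 2.4.4.3.1: "Sex and height will be included as covariates in the models, if the endpoint belongs to spirometry parameters".
- Section 11.4.2.2.1: "Sex, height and ethnicity will also be included as covariates in the models for spirometry parameters".
- Clinical Trial Summary, statistical considerations: "Sex, height, and ethnicity will also be included as covariates in the models for spirometry parameters". Just before this, the general covariate list is qualified by "unless otherwise specified (details will be documented in SAP".

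**SAP 2.4.4.3.1.** For continuous endpoints other than ACQ-7-IA and FeNO, the model holds treatment, age, weight category, region, eosinophil level (type 2 population only), FeNO level, ICS dose level, visit, treatment by visit, baseline value and baseline by visit. The one spirometry-specific addition is: "Ethnicity will be included as the covariate only in the models for spirometry parameters, specifically". Sex and height are not mentioned.

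**Endpoints covered.** SAP 2.1.3.2 lists the other lung function measures as "absolute and relative FEV1, AM/PM peak expiratory flow, FVC, forced expiratory flow (FEF) 25-75"% and post-bronchodilator % predicted FEV1.

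**Logged changes.** SAP 1.6, Table 2: "For analysis of Pre-bronchodilator % predicted FEV1, covariates of age, sex, and baseline height are removed from the model". Table 3 has a single entry, for the key secondary endpoint model, with the reason: "The effect of age, sex, and height on the predicted FEV1 have already been accounted in the predicted FEV1 calculation equation".

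**The concern.** Protocol and SAP specify different models for the same endpoints, and the stated reason for dropping sex and height does not carry over. A % predicted value has already been scaled for age, sex and height. A volume in litres or a flow rate has not. SAP 2.4.4.3.1 also keeps age while dropping the other two, so it follows neither the protocol nor the logged removal of all three. The documents do not show whether this was intended.

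At stake are consistency with the protocol and, possibly, some precision. SAP 2.4.4.3.1 promises 95% confidence intervals and p-values for these endpoints, so the covariate set should be settled and explained.

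**Working it through.** **Step 1: compare the texts** for a spirometry endpoint not expressed as % predicted.

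| Covariate | Protocol | SAP 2.4.4.3.1 |
|---|---|---|
| Age | yes | yes |
| Sex | yes | no |
| Height | yes | no |
| Ethnicity | in the Summary and 11.4.2.2.1; not in 11.4.2.2.3 | yes |

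The SAP drops sex and height, and no logged reason covers these endpoints. If the ethnicity sentence is read as confining ethnicity to spirometry models, sex and height are still absent from the section.

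**Step 2: cost of including two covariates that explain nothing.** SAP 1.1 plans about 345 patients in the type 2 population and about 255 with eosinophils ≥0.3 Giga/L. With q covariate terms already in the model, two more multiply the variance by about (N − q − 3)/(N − q − 5). In the type 2 population q = 9: age, weight, region (2), eosinophils, FeNO, ICS dose, baseline value, ethnicity. In the other population eosinophils drop out and q = 8.
- N = 345: 333/331 = 1.0060, or 0.30% of the standard error.
- N = 255: 244/242 = 1.0083, or 0.41%.

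Inclusion breaks even when the partial R-squared of sex and height is 1 − 1/1.0060 = 0.60% or 1 − 1/1.0083 = 0.82%.

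**Step 3: possible gain, under assumptions.** The documents give no SDs, so every input here is assumed, as a percentage of the endpoint mean. Let w be the within-patient SD, b the between-patient SD unrelated to size, s the SD of body-size effects given age, k the share of size variance explained by weight category, and r the share of the remainder explained by sex and height. At a single visit, the variance of change given baseline is

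2w² − w⁴/(V + w²),

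with V = s²(1 − k) + b² without sex and height, and V = (1 − r)s²(1 − k) + b² with them.

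Central case (s = 10, k = 0.35, r = 0.85, b = 14, w = 9):
- Without: V = 65 + 196 = 261; 162 − 6561/342 = 142.8.
- With: V = 9.75 + 196 = 205.75; 162 − 6561/286.75 = 139.1.
- Standard error ratio √(142.8/139.1) = 1.013. Net of Step 2, omission costs 1.0% at N = 345 and 0.9% at N = 255.

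Grid of 243 cases: s = 8, 10, 12; k = 0.2, 0.35, 0.5; r = 0.7, 0.85, 1.0; b = 12, 14, 16; w = 7, 9, 11. Net increase in the standard error from omission:

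| | Min | Median | Max | Cases under 1% | Cases favouring omission |
|---|---|---|---|---|---|
| N = 345 | −0.02% | 0.91% | 4.07% | 54% | 1 |
| N = 255 | −0.13% | 0.80% | 3.96% | 62% | 5 |

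**Step 4: relax one assumption.** Step 3 gives every child in an arm the same true change. Adding a true-change SD u, unrelated to sex or height, adds u² to both variances and shrinks the gain.

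| u | Median, N = 345 | Median, N = 255 | Cases favouring omission (345 / 255) |
|---|---|---|---|
| 6 | 0.65% | 0.54% | 6 / 18 |
| 9 | 0.46% | 0.35% | 16 / 41 |
| 12 | 0.29% | 0.18% | 40 / 70 |

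**The case against.** The strongest reply is that the SAP was entitled to do this. The protocol summary defers covariate details to the SAP, SAP 2.4.4.3.1 gives a complete list, and section 1.6 claims to summarise only major changes, so a covariate edit for untested endpoints need not appear there. The protocol also disagrees with itself about ethnicity, so one list had to be chosen. All of this stands. None of it supplies a reason for dropping sex and height from these endpoints.

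A second reply is that baseline FEV1 or FVC already carries much of a child's size, and that the percentages rest on invented inputs. This also largely stands. The grid takes r only from 0.7 upwards, which favours a gain; Step 4 lowers the medians; and the formula is for a single visit, not the planned repeated-measures model. The shares of cases describe the grid, not this trial.

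A third reply concerns scope. The units argument does not clearly reach relative FEV1, which the documents do not define. It is covered only because the protocol's rule applies to spirometry parameters generally. Clinic PEF is measured, but the listed endpoint is AM/PM PEF, which SAP 2.1.3.4 treats as a daily diary-meter measure.

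A reader might infer a protocol violation, a biased comparison or an inflated type I error. The documents support none of these. The deferral clause permits the change, randomisation protects the comparison, and these endpoints are in neither Table 9 nor Table 10.

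**Conclusion.** The difference is real and minor. Two covariates that the protocol names are missing from SAP 2.4.4.3.1 for absolute FEV1, FVC and FEF25-75%, and the only logged reason cannot apply to them. The consequence is at most a possible small loss of precision in nominally tested comparisons: about 0% to 4% of the standard error under assumed inputs, typically under 1%, with no gain from inclusion if the partial R-squared is below 0.60% (N = 345) or 0.82% (N = 255). The documents do not show that sex or height predicts change given baseline value, age and weight category, so the loss is a possibility and cannot be quantified from them. The textual finding does not depend on these assumptions. No sample size, power statement or confirmatory test is affected.

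**What to change.** In SAP 2.4.4.3.1, state that for spirometry endpoints not expressed as % predicted (absolute FEV1, FVC, FEF25-75%, and relative FEV1 under the protocol's general rule) the model also includes sex and baseline height, in addition to age and ethnicity. Specify baseline height: height is measured at every visit (SAP 2.1.4.4), and later values are post-randomisation. State whether AM/PM PEF from the diary meter counts as a spirometry parameter. Do not name clinic PEF, which is not a listed endpoint. If the omission was intended, give a reason that fits these endpoints.

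The cost is one or two sentences and two degrees of freedom, 0.3% to 0.4% of the standard error if the covariates explain nothing. Both variables are already collected.

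A separate alignment correction: SAP Table 7 still lists age, sex and baseline height for the key secondary model. It should match Table 3, the text of 2.4.4.2.1 and the sample code there, all of which omit them.

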2.4.4.3.2 Time to event variables

A Cox regression model and Kaplan-Meier method will be used to assess treatment differences in time to events (defined in [Section 2.1.3.2](#)) in the Type 2 inflammatory asthma phenotype and baseline blood eosinophils ≥ 0.3 Giga/L populations.

When performing the time-to-event analyses in the Type 2 inflammatory asthma phenotype population, the model will include the time to the first event as the dependent variable, and treatment groups, age, baseline weight (≤ 30 kg, > 30 kg), region, baseline eosinophil level, baseline FeNO level, baseline ICS dose level and number of severe exacerbation events within 1 year prior to the study as covariates. When performing the time-to-event analyses in the baseline blood eosinophils ≥ 0.3 Giga/L population, the baseline eosinophil level will be removed from the model covariates. Hazard ratio will be estimated for the comparison between dupilumab and placebo. The Kaplan-Meier method will be used to derive the probabilities that a patient would experience events up to Week 12, 24, 36 and 52 per each treatment group. Kaplan-Meier curves will be generated; quartiles and point probabilities will be calculated. Interval estimates will be calculated using 95% point-wise confidence intervals.

Sample SAS codes can be found as below:

```
proc phreg data=timeto;
class weight eosblgpn eosblgpn1 fenoblgpn ics trt01pn cntygr1n /param=GLM;
model aval*CNSR(1) =trt01pn weight age eosblgpn1 fenoblgpn ics cntygr1n asmanum;
contrast 'dupilumab vs Placebo rate ratio' trt01pn -1 1
run;
```

For these secondary endpoints, the primary estimand and details about the intercurrent events strategy and missing data handling are presented in

Table 8 as below. Additional secondary objectives/endpoints are not included in this table but would be handled with a similar strategy as the endpoint type (ie, count, continuous, proportion, time-to-event).

Table 8 - Summary of primary estimand for secondary endpoints

Endpoint Category (estimand)	Estimands			
	Endpoint	Population	Intercurrent event(s) strategy and missing data handling	Population-level summary
Primary objective: The primary objective is to evaluate the efficacy of dupilumab in children 6 to <12 years of age with uncontrolled persistent asthma				
Secondary endpoint (treatment policy)	Time to first severe exacerbation event during 52-week treatment period	Type 2 inflammation phenotype; Patients with baseline blood eosinophils ≥ 0.3 Giga/L population	The intercurrent events will be handled as follows: Discontinuation of study treatment before Week 52: Off-study treatment data up to Week 52 will be included in the analysis (treatment policy strategy). In addition, the missing data imputation rules are as follows: Discontinuing the study follow-up before Week 52: Analyses will be censored at the time of study discontinuation.	In patients with Type 2 inflammatory asthma phenotype, this time-to-event endpoint will be analyzed using the Cox proportional hazards model, include the time to the first event as the dependent variable, and treatment groups, age, baseline weight, region, baseline eosinophil level, baseline FeNO level, baseline ICS dose level and number of severe exacerbation events within 1 year prior to the study as covariates. The hazards ratio, its 95% confidence interval and p-value will be reported. Kaplan-Meier curves will be also provided. In patients with baseline blood eosinophils ≥ 0.3 Giga/L, the analysis will remain same as above except that the covariate of baseline eosinophil level will be removed.
Secondary endpoint (treatment policy)	Proportion of participants who reached MCID (responders) defined as change from baseline in ACQ-7 ≤ -0.5 at Week 12, 24, 36 or 52.	Type 2 inflammation phenotype; Patients with baseline blood eosinophils ≥ 0.3 Giga/L population	The intercurrent events will be handled as follows: Discontinuation of study treatment before the visit to be analyzed: Off-study treatment data will be included in the analysis (treatment policy strategy). In addition, the missing data imputation rules are as follows: In addition, having missing data at the visit to be analyzed, patients will be considered as non-responders	In patients with Type 2 inflammatory asthma phenotype, this endpoint will be analyzed using logistic regression with treatment, age, baseline weight, region (pooled country), baseline eosinophil level, baseline FeNO level, baseline ICS dose, level, and baseline ACQ-7 score as covariates. The number (n) and percentage (%) of responders of each arm, odds ratio between treatment and placebo arms, 95% confidence interval and P value will be reported. In patients with baseline blood eosinophils ≥ 0.3 Giga/L, the analysis will remain same as above except that the covariate of baseline eosinophil level will be removed.

